9.7.2.2 RISK OF SEVERE COMPLICATIONS OF DIARRHOEA

If the validation results of cases is satisfactory (positive predictive value of EMRs $\geq 95\%$ and negative predictive value $\geq 99\%$), then information from the whole cohort would be used to estimate the incidence of SCD in the cohort of IBS-C patients, as well as the relative risks of SCD and the exposures of interest (mainly exposure to linaclotide) using the Cox proportional hazard model. Additionally, the nested case-control analysis will be conducted, and conditional logistic regression will be used as indicated in Section 9.7.3.1.

Alternatively, if the validation results show positive predictive value of EMRs $< 95\%$ or negative predictive value $< 99\%$, then only the nested case-control analysis will be conducted, and conditional logistic regression will be used in place of Cox regression.

The corresponding regression models will be used to identify risk factors associated with risk of SCD. Multivariate regression models will be fitted to identify the effects of various baseline variables on the probability of having SCD. A set of 10 to 20 plausible candidate models will be proposed and fitted to the data. Models will be ranked according to Akaike's Information Criterion (AIC) and the best model will be selected. If several models prove to perform well, these will be averaged to produce a final model. Some iteration between choosing candidate models and data analysis will likely be necessary: in the case of Cox regression, due to the need to check that the proportional hazards assumption holds for each candidate model, and in all scenarios due to the iterative nature of the information theoretic model-building approach.

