Using the latest available information, the sample size across the three countries is approximately 329,000 patients with IBS-C or potential IBS-C, with an exposure to linaclotide rate ranging from 1% to 4%. If the results of the validation of cases are satisfactory with positive predictive value of SCD algorithms in the UK and Spain $\geq 95\%$, information from the whole cohort will be used to estimate risk of developing SCD across the groups of patients with or without linaclotide exposure, under a cohort study design. If the positive predictive values are $< 95\%$, a case-control analysis will be performed. Assuming the percentage of patients exposed to linaclotide among controls is around 1%, a minimum of 401 case-control pairs would be required to detect an $OR \geq 4$ and 745 possible case-control pairs to detect an $OR \geq 3$ with 80% power, under a matched case-control study design. Within the total IBS-C cohort, it is expected to accrue approximately 11,800 algorithm-identified, potential SCD cases. The final number of case-control pairs to be included in the analyses will depend on the performance of SCD algorithms and case validation results and is expected to be sufficient to detect an $OR \geq 3$ at 80% power, given the number of potential SCD cases identified by the algorithms.

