8.2 OPERATIONAL OBJECTIVES

- To estimate the risk (case-control OR) of SCD (case) among patients with IBS-C (source population) who received linaclotide prescription vs those who did not, controlling for other potential SCD risk factors (socio-demographics, comorbidities [up to 15], co-medications [up to 15] and other potential variables of interest [up to 10])
- To describe the crude incidence of diarrhoea among patients with IBS-C (source population)

If allowed by the results of the cases and controls validation as discussed below:

- To describe the crude incidence of SCD among patients with IBS-C (source population) prescribed linaclotide (first-time users)
- To describe the crude incidence of SCD among patients with IBS-C (source population) prescribed linaclotide (first-time users) who are at increased risk of SCD:
 - o Patients ≥ 65 years
 - o Patients with hypertension, diabetes, or cardiovascular disease diagnostic codes

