In response to the MAH's proposal, in the preliminary assessment report for the PASS protocol amendment submission (3rd Oct 2022), PRAC requested the MAH to extend the UK observational period up to the most recent possible date in order to include all available data and to revise the data collection period in the milestones accordingly, without further postponement of the final report (Q3 2023). The MAH contacted CPRD to confirm next steps for data extraction and validation study rerun. CPRD required that the MAH submits a new protocol to the CPRD review committee before requesting the new datasets and re-running the validation study. This is due to the change of dataset from CPRD GOLD to CPRD GOLD and CPRD Aurum, and the change of the observational period. The MAH submitted a new protocol to CPRD in April 2023 and expected to receive approval and the new datasets in Q3 2023. However, the actual process from application submission to data access took almost 12 months and the final data cut was eventually delivered in March 2024. The identification of new potential SCD cases as well as the initiation of validation activities have been completed in Q2 2024.

The validation of the diagnosis and SCD cases ended in Q2 2020 in Spain and expected to end in Q3 2024 in the UK. There is no validation study in Sweden. This study period is expected to allow for sufficient follow-up (long-term safety assessment) for those enrolled during the first period after linaclotide launch and for any subpopulations of interest (those with increased risk of SCD) to have the opportunity to accrue a sizable number of subjects for descriptive purposes. Please refer to Section 9.5 *Study Size* and Section 9.7 *Data Analysis* below.

[figure not shown]
The IBS-C cohort entry date for each cohort member will be defined as the date IBS-C criteria are first fulfilled or 01 February 2013 in Sweden, 13 May 2013 in the UK, and 01 September 2014 in Spain (linaclotide launch dates), whichever is the latest.

The follow-up period for each study subject in the IBS-C cohort will be from the cohort entry date to the earliest of the following (end of follow-up date; one day is the minimum follow-up (Figure 1):

- End of the study period
- Disenrollment from the database (date of transfer out of the practice or the PCP or Sweden)
- Date of last data collection for the practice
- Death
- Index date

The baseline period is the ≥ 12 -month period before IBS-C cohort entry date.

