9.7.3 NESTED CASE CONTROL ANALYSES

9.7.3.1 RISK OF SEVERE COMPLICATIONS OF DIARRHOEA

Conditional logistic regression analyses will be used to estimate the relative risk (case control OR) of SCD among patients who were treated with linaclotide, had a prescription for laxatives, were ≥ 65 years old, and had a history of hypertension, diabetes or cardiovascular disease diagnostic codes (i.e., SCD occurrence is the outcome variable [yes/no], and the independent variables of main interest are whether the patient has a prescription for linaclotide, a prescription for laxatives, the patient is ≥ 65 years old, and the patient has hypertension, diabetes or cardiovascular disease diagnostic codes, all of them at index date, or not). The same multivariate regression modelling approach (as described in Section 9.7.2.2) will be followed.

For the algorithm-identified cases and controls that are not validated, sensitivity analyses will be performed to test different scenarios by treating these unconfirmed SCD events as either missing, cases or controls, respectively.

Statistical analyses will be conducted using SAS[®] statistical software.

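### The AIC selection and averaging rule in Section 9.7.2.2 also governs the main linaclotide estimate, and nothing keeps linaclotide or a core confounder set in every candidate model

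*Protocol*

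**What the plan says.** The first operational objective in Protocol Section 8.2 is the case-control odds ratio of SCD in patients "who received linaclotide prescription vs those who did not, controlling for other potential SCD risk factors".

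Section 9.7.2.2 sets the modelling rule for both the Cox and the conditional logistic analyses:

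- On what the regressions contain: "Multivariate regression models will be fitted to identify the effects of various baseline variables on the probability of having SCD".
- On how many are tried, without listing them: "A set of 10 to 20 plausible candidate models will be proposed and fitted to the data".
- On the choice among them, ranking is by AIC, "and the best model will be selected. If several models prove to perform well, these will be averaged to produce a final model".
- On changing the candidates during the analysis: "Some iteration between choosing candidate models and data analysis will likely be necessary". For Cox regression the reason given is the proportional hazards check; for all scenarios it is the nature of the model-building approach.

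Section 9.7.3.1 carries this into the case-control analysis: "The same multivariate regression modelling approach (as described in Section 9.7.2.2) will be followed". It names linaclotide among the variables of main interest, but does not say that it stays in every candidate. The case-control analysis runs whatever the validation result. The Cox analysis runs only if PPV is at least 95% and NPV at least 99%.

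On timing, Section 9.2.1.4 puts baseline before cohort entry. Cohort entry "will be defined as the date IBS-C criteria are first fulfilled or 01 February 2013 in Sweden" (or the launch date of the other two countries), whichever is later. Section 9.3.2 defines current, non-current and never use for cases and controls at the index date. Section 9.2.1.3 draws controls from the case's risk set.

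**The concern.** One modelling rule serves two different aims. For exploring risk factors, ranking candidates by AIC is reasonable. For estimating the adjusted effect of a named exposure it is not: AIC rewards prediction of SCD, not control of confounding. An exposure present in only 1% to 4% of patients (Section 4.8) adds little to overall fit even when its effect is real.

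Three consequences follow if a candidate without linaclotide is allowed. The term can be dropped, leaving no estimate for the main objective. If models are averaged with a zero coefficient where linaclotide is absent, its odds ratio is pulled towards 1. If the term survives selection, the estimate tends to be too large and its usual confidence interval ignores the selection. In a safety study, a lost or shrunken harm signal is the more serious of these errors. Even with linaclotide in every candidate, the confounders it is adjusted for would still be chosen on the data.

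The Cox branch has a second, narrower problem. Its regression is described in terms of baseline variables, while linaclotide mostly starts after cohort entry.

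**Working it through.** **Inputs.** From Sections 4.8 and 9.5.2: 1% of controls exposed, 1:1 matched pairs, two-sided α 0.05, 80% power, 401 pairs for OR 4, 745 pairs for OR 3, and about 11,800 potential cases before validation. Assumptions: linaclotide is a single yes/no term; one candidate contains it and an otherwise equal one does not; averaging uses Akaike weights with a zero coefficient where the term is absent.

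**Step 1: reproduce the plan's figures.** With P = OR/(1+OR), the required discordant pairs are m = [1.960/2 + 0.842·√(P(1−P))]² / (P−0.5)². The probability that a pair is discordant is pe = p0(1−p1) + p1(1−p0), where p1 = p0·OR/(1+p0(OR−1)).

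- OR 3: m = 28.92, p1 = 0.02941, pe = 0.03882, so 28.92/0.03882 = 744.9, giving 745 pairs.
- OR 4: m = 19.26, p1 = 0.03883, pe = 0.04806, so 19.26/0.04806 = 400.8, giving 401 pairs.

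Both agree with Table 3, so the sample sizes are not in dispute.

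**Step 2: when AIC drops the term.** One extra parameter costs 2 AIC units, so linaclotide is dropped when its likelihood-ratio statistic is 2 or less. With n discordant pairs, x of them with the case exposed, LR = 2[x·ln(2x/n) + (n−x)·ln(2(n−x)/n)].

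At 745 pairs and a true OR of 2, about 22 discordant pairs are expected. A 14:8 split (observed OR 1.75) gives LR = 1.66 and is dropped. A 15:7 split (observed OR 2.14) gives LR = 2.98 and is kept. One pair decides.

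**Step 3: averaging.** The weight is w = 1/(1+exp(−(LR−2)/2)) and the averaged log OR is w·ln(OR), with 0.5 added to each cell.

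**Step 4: results** over the exact binomial distribution of n and x. ORs are geometric means.

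| Pairs | True OR | Expected discordant pairs | Dropped | Averaged OR | Mean OR if kept and above 1 |
|---|---|---|---|---|---|
| 401 | 4 | 19.3 | 8% | 3.6 | 4.4 |
| 745 | 3 | 28.9 | 8% | 2.7 | 3.2 |
| 401 | 3 | 15.6 | 26% | 2.5 | 3.8 |
| 401 | 2 | 11.8 | 59% | 1.6 | 3.7 |
| 745 | 2 | 21.9 | 43% | 1.7 | 2.7 |
| 2,950 | 2 | 86.7 | 4% | 1.9 | 2.0 |
| 11,800 | 2 | 347.0 | under 0.1% | 2.0 | 2.0 |
| 11,800 | 1.5 | 290.6 | 2% | 1.5 | 1.5 |

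The 2,950 row is one quarter of 11,800, for illustration. As a cross-check, 80% power corresponds to a noncentrality of (1.960+0.842)² = 7.85, and a noncentral chi-square on 1 df falls below 2 with probability 8.3%. For the three-level user variable (2 df, threshold 4) it is 15.4%.

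With linaclotide forced into every candidate, the drop probability is 0 and the mean estimate stays at the true value (3.0 and 4.0 at the two design points).

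**Step 5: the Cox wording.** A patient who enters on the launch date cannot have marketed linaclotide in the baseline period. Read literally, a model on baseline variables counts that patient's later use as unexposed. An incident patient, who enters later, could have had a prescription before the IBS-C codes were complete, so the exposure is not empty for everyone.

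**The case against.** Section 9.7.3.1 names linaclotide as a variable of main interest, and a sensible analyst would put it in every candidate. The SAP listed in Annex 1 may say so. That reading is natural, and under it the term is neither dropped nor averaged with zero. But the protocol itself fixes the AIC rule, the averaging and the iteration, makes no exception for the main exposure, and leaves the confounder set open.

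The numbers also depend on the scenario. Section 4.8 calls 401 pairs a minimum, Section 9.2.1.3 allows up to four controls per case, and Table 3 asks for 2,321 pairs at OR 2. Much of the loss at OR 2 with 401 or 745 pairs is therefore plain lack of power. With half of the potential cases confirmed (5,900 pairs, an assumption), OR 2 is dropped about 0.1% of the time. This stands, and limits the concern to a low confirmed count or a modest effect. Section 4.8 makes the final count depend on validation and expects only enough pairs for OR 3 or more.

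A reader might also infer immortal-time bias, because Section 4.8 speaks of estimating risk "across the groups of patients with or without linaclotide exposure, under a cohort study design". If exposure were coded ever/never from entry, a first prescription 1 or 3 years into 5 years of follow-up (assumed) would multiply the ratio by about 1 − 1/5 = 0.8 or 1 − 3/5 = 0.4. The documents do not support stating this as a defect. No passage codes later use back to entry, that sentence says nothing about allocating person-time, and the descriptive rates in Section 9.7.2.1 run from first prescription. Index-date exposure with risk-set sampling protects the case-control estimate.

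**Conclusion.** The selection point holds and should be corrected before analysis. As written, an open, data-revised candidate set ranked by AIC determines the linaclotide estimate in both analyses. At the design values the damage is modest: about 8% dropped, and averaged ORs of about 3.6 for a true 4 and 2.7 for a true 3. At a true OR of 2 with 401 or 745 pairs it is large: 59% or 43% dropped, and an averaged OR of about 1.6 to 1.7. It is small if most of the 11,800 potential cases are confirmed. These figures assume 1:1 pairs, 1% exposure, a candidate without linaclotide and zero-filled averaging. The pull is towards 1, not to 1.

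The timing point holds only for the Cox analysis, and only as a mismatch between baseline variables and an exposure that mostly starts after entry.

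**What to change.** In Sections 9.7.2.2 and 9.7.3.1:

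- Take the linaclotide estimate from one pre-specified model containing linaclotide and a fixed confounder list drawn from Section 9.3.2.
- Limit AIC selection and averaging to the exploratory risk-factor objective, with linaclotide forced into every candidate.
- State that in the Cox model linaclotide is time-varying from the first prescription, with earlier time counted as unexposed. The case-control model already uses index-date exposure and needs no change on this point.

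Limiting the number of confounders by the count of exposed cases, or summarising them in one risk score, is optional.

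The cost is a few sentences of protocol and SAP text and no new data. The confidence interval may be slightly wider than from an AIC-trimmed model.

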9.7.3 NESTED CASE CONTROL ANALYSES

9.7.3.1 RISK OF SEVERE COMPLICATIONS OF DIARRHOEA

Conditional logistic regression analyses will be used to estimate the relative risk (case control OR) of SCD among patients who were treated with linaclotide, had a prescription for laxatives, were ≥ 65 years old, and had a history of hypertension, diabetes or cardiovascular disease diagnostic codes (i.e., SCD occurrence is the outcome variable [yes/no], and the independent variables of main interest are whether the patient has a prescription for linaclotide, a prescription for laxatives, the patient is ≥ 65 years old, and the patient has hypertension, diabetes or cardiovascular disease diagnostic codes, all of them at index date, or not). The same multivariate regression modelling approach (as described in Section 9.7.2.2) will be followed.

For the algorithm-identified cases and controls that are not validated, sensitivity analyses will be performed to test different scenarios by treating these unconfirmed SCD events as either missing, cases or controls, respectively.

Statistical analyses will be conducted using SAS[®] statistical software.

9.8 QUALITY CONTROL

Standard operating procedures at each research centre will be used to guide the conduct of the study. These procedures include internal quality audits, rules for secure and confidential data storage, methods to maintain and archive project documents, quality-control procedures for programming, standards for writing analysis plans, and requirements for senior scientific review.

Aggregate results will be presented in accordance with data privacy policy and small numbers ($n < 5$) will be blinded.

All work will be subject to quality-control and documentation procedures to make certain that the final report is accurate and thorough, and the analyses can be reproduced. If the data do not permit an analysis as planned (e.g., through insufficient sample size in a subgroup analysis) or if clarifying analyses are required (e.g., an unexpected result that could be explained by a subgroup analysis), Evidera staff will inform AbbVie and include the additional information and results in the report. All key study documents, such as the analysis plan, abstraction forms, and study reports, will undergo quality-control review, senior scientific review, and editorial review.

A quality-assurance audit of this study may be conducted.

9.9 LIMITATIONS OF THE RESEARCH METHODS

Categorisation of patients with IBS into IBS-C, IBS-D, or IBS-M might be challenging. Similarly, the classification into mild, moderate, and severe IBS-C is not recorded in the databases and is expected to be available only for a fraction of patients. Differentiation between IBS-C and chronic constipation will also be challenging. As a consequence, some degree of misclassification is to be expected.

In the databases, we may miss some occurrences of safety endpoints (e.g., electrolyte imbalance) if they are not explicitly recorded; however, this is expected to affect only patients with complications of diarrhoea of milder severity.

The use of over-the-counter medications for the treatment of IBS-C-related symptoms, constipation, and diarrhoea is acknowledged as another study limitation. We will include over-the-counter medications, such as laxatives, when this information is recorded in the databases and reported by PCPs answering the study validation questionnaire. However, we expect under-recording of over-the-counter medications in the databases, and therefore the overall use of laxatives will be incompletely reflected. If the extent of misclassification of laxative exposure is different among cases and controls then some of the odds ratios could be biased and this limitation should be taken into account when the results are interpreted.

The CPRD provides a large, diverse, and representative sample of UK people using primary care services, which allows for generalizability of the study findings to the broader UK population. The General Practice Research Database (GPRD), predecessor to CPRD, has been widely used for observational studies, with over 890 studies published to date in peer-reviewed journals. The SIDIAP database includes information for 90% of the population in Catalonia, a region in northeast Spain, and resembling the data collected by the UK databases. One limitation is that date of prescription is only available for the first prescription and, thereafter, only an approximate date of dispensation is available. For Sweden, the NPR and PDR cover the entire Swedish population and have been previously used in observational studies including drug utilisation ones. However, no primary care data will be available, so diagnoses will be those determined by a specialist, which are expected to be required for the variables of interest for this study. The PDR is not complete with regard to drugs used in nursing homes.

According to the National Board of Health and Welfare, about 1% of people aged 65–79 years live in nursing homes, and about 20% of people aged 80 or more years live in nursing homes in Sweden [Socialstyrelsen]. This may be reflected in potential lower numbers of elderly patient using linacotide identified in Sweden.

The validity of research findings based on CPRD data and data from the other databases depends on the quality and completeness of the data recorded. We are only able to identify comorbidities for which the patient has consulted their GP. Referrals are not always uniformly coded and may appear as free-hand text or letters within the database.

Interval censoring might have an impact on the precision of the results.

Additionally, the proposed linked data sources (i.e., HES OP, HES AE and HES APC) have different linkage coverage periods. In particular, HES OP and HES AE linkage periods are considerably shorter than that of HES APC. This might increase the risk of SCD cases being underestimated. Finally, potential SCD are not classified by severity.

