Information about treatment use will be obtained from the Swedish PDR. Its coverage is close to 100% of all prescribed medicines from both primary health care centres and outpatient specialists dispensed to the Swedish population, and information is available since July 2005 (Wettermark et al., 2007). The register contains data on the substance, brand name, formulation, and package, dispensed amount, dosage, expenditure, and reimbursement as well as date of dispensing. Dispensation of over-the-counter (OTC) medications is not included.

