For each medication of interest, a patient (cases and controls) will be classified at the index date according to the following user experience (time window of exposure to the medication):

- Current user, if there was a prescription or dispensation of the medication of interest with supply until the index date or supply that ended in the 90 days before the index date.
- Non-current user, if the last prescription or dispensation was issued longer than 90 days before index date
- Never user, if there is no prescription or dispensation history for that medication.

The main exposures or potential risk factors of interest are:

- Linaclotide user experience category as described above
- Laxatives user experience category as described above

Additionally, other variables listed above will be included in the analyses. Duration of medication use for each of the medications of interest will also be used (defined as time since the first documented prescription without discontinuation until the case or control index date).

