9.3.4 VALIDATION OF THE DIAGNOSIS AND SAFETY ENDPOINTS

Information on IBS-C is not well-captured by standard diagnosis codes. SCD is also not coded as such in the databases. Therefore, IBS-C and SCD will be validated by the physicians treating the patients selected as cases or as controls. This will require additional primary data collection from GPs that is possible in the UK with the use of CPRD.

The process in the UK would consist of asking cases' attending GPs to confirm the type of IBS. All cases (patients with IBS-C experiencing SCD) will be characterised in further detail through contact with their PCPs. A questionnaire will be mailed to the GP with whom each identified subject is registered to validate both diagnoses (IBS and SCD [if applicable]; please refer to [Annex 3](#)).

The feasibility of using this questionnaire to collect validation information about cases was evaluated through a pilot study with a small number of physicians in the UK. This UK pilot study targeted a group of 25 PCPs to test the questionnaire and contribute to its development. The section, *Pilot Study Summary Report*, in Annex 3 reports on the pilot study conduct. This pilot study included additional questions to PCPs about preferred codes or code combinations used to record diagnoses of patients with IBS-C.

Although it was originally planned for the validation study to also be undertaken in Spain using GP questionnaires, since 2018, SIDIAP no longer allows the possibility to contact physicians for extracting extended additional information on the patient through long- questionnaires. However, there is the possibility of a text review of the primary care records. This text review can be used to validate cases of interest, conducted by IDIAP's clinical researchers. For this study, it is recommended by the data custodians that a review of free-text in the patient's medical records is conducted to improve the validity of the actual study, in place of the previously planned validation strategy using questionnaires to GPs. This free-text review is made after an anonymisation process of the clinical records and a natural language processing of the text.

We will validate our outcome identification algorithm by calculating the positive predictive value and the negative predictive value in both countries.

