FVG is in the northeastern part of Italy and has approximately 1.2 million inhabitants. In Italy, all citizens are covered by taxed-based public health insurance. The hospital discharge database of the FVG region of Italy routinely collects data from all hospitals in the region and includes information on patients' sociodemographic characteristics and treatment received during hospitalization. Given that the LHUs can capture the same data, in a larger population, this database was excluded.

Pilot Study Summary Report

Background

AbbVie is planning a nested case-control study to assess the safety of linaclotide, authorised for the symptomatic treatment of moderate-to-severe irritable bowel syndrome predominantly with constipation (IBS-C) in adults. The study goal is to assess the risk of severe complications of diarrhoea (SCD) among patients with IBS-C exposed to linaclotide or other treatments, controlling for potential risk factors. This study will be conducted in the United Kingdom (UK), amongst other countries, using data from the Clinical Practice Research Datalink (CPRD).

Information on IBS-C and SCD is not well captured in electronic data sources by standard diagnosis codes, therefore, the study plan includes additional primary data collection from general practitioners (GPs) to validate IBS-C diagnoses and potential SCD events identified through an algorithm based on electronic records. This type of additional data collection is feasible in the UK with the use of the CPRD. For cases and controls (or a sample of them, depending on the number of cases and controls), validation data will be collected through a questionnaire mailed to the attending GP with whom each identified study subject is registered.

Before using the questionnaire to collect information about IBS-C diagnoses and potential SCD events in the safety study, we conducted a pilot study to test this questionnaire with a small number of physicians in the UK.

Objective and Rationale

The objective of the pilot study was to assess the face validity of a questionnaire to collect information from PCPs to validate:

1. The correct identification of the study population (cohort of patients with IBS-C)
2. The patients experiencing the endpoints of interest

Study Design

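### Section 9.9 brings questionnaire-reported over-the-counter laxatives into an exposure defined elsewhere from prescription records, using a source that not every case and control has

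*Protocol*

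**What the plan says.** Protocol section 9.3.2 names two main exposures. One is linaclotide; the other is "Laxatives user experience category as described above". The category rests on records: "Current user, if there was a prescription or dispensation of the medication of interest with supply until the index date" (or supply ending within the preceding 90 days). The same section defines the medication confounders by prescriptions. Section 9.7.2.1 takes exposure to linaclotide and laxatives from prescription data in the databases. The conditional logistic model in section 9.7.3.1 lists among its main terms "a prescription for laxatives, the patient is ≥ 65 years old". None of these definitions has an over-the-counter (OTC) element.

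Section 9.9 adds one: "We will include over-the-counter medications, such as laxatives, when this information is recorded in the databases and reported by PCPs answering the study validation questionnaire". It goes on to expect under-recording of OTC products in the databases. It also warns that some odds ratios could be biased if laxative misclassification differs between cases and controls, and leaves this to interpretation.

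On who is surveyed, sections 9.2.1.3, 9.3.4 and 9.7.1 plan GP validation of both cases and controls in the UK. Section 9.3.4 also says "All cases (patients with IBS-C experiencing SCD) will be characterised in further detail through contact with their PCPs", with no matching statement for controls. The pilot report in Annex 3 refers to cases and controls, "or a sample of them, depending on the number of cases and controls". Spain uses free-text review (9.2.1.3, 9.3.4). Sweden has no validation study (9.2.1.4), and for its drug register section 4.7 says "Dispensation of over-the-counter (OTC) medications is not included".

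**The concern.** The protocol gives two accounts of how a main exposure is measured. One relies on records that exist for every subject in a database. The other adds information that exists only where a UK GP has returned a form.

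If forms are returned more often for cases than for controls, the added OTC use raises measured laxative exposure more in cases. The laxative OR then moves upwards even when there is no true association. Laxative use sits in the same model as linaclotide, so uneven measurement could also disturb the adjustment of the linaclotide OR; the documents give no basis for the size or direction of that effect. The variable would also mean something different in the UK from what it means in Spain and Sweden, which matters if the countries are pooled under section 9.7.

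OTC use is unlikely to be trivial, since section 9.3.2 expects most patients to treat themselves.

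**Working it through.** **1. The two definitions.** Sections 9.3.2, 9.7.2.1 and 9.7.3.1 use prescription or dispensing records. Section 9.9 adds OTC use. A product bought without prescription produces no prescription record, so the section 9.9 rule does not fit the variable defined in the other three.

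**2. What the rule means.** The condition is "when this information is recorded in the databases and reported by PCPs answering the study validation questionnaire". The word *and* can be read in two ways:
- Both conditions are required. OTC use then counts only for subjects with a form, and only if it is also in the database.
- They are two separate sources. Database-recorded OTC use then counts for everyone, and the form adds to it.

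On either reading, part of the exposure depends on a returned form.

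**3. Who can have a form.** Only UK subjects can. Section 4.10 reports very low GP response, without a rate or a case-control split. A case confirmed by GP questionnaire has a form by definition; its matched controls, up to four under section 9.2.1.3, need not. No passage requires equal coverage within matched sets.

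**4. Whether the form measures the right thing.** Questions 2 to 4 of the Annex 3 questionnaire ask about treatment for IBS-C on or just before the IBS-C event date. Exposure is classified at the index date, which is the date of the diarrhoea episode (9.2.1.2). Questions 6 and 7 ask only whether the treatments already listed were stopped because of the diarrhoea. No question mentions OTC products.

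**5. Possible size.** The plan states no figure to reproduce. It gives no OTC laxative prevalence, response rate or capture rate, so every input here is an assumption:
- prescribed laxative use *r*: 20% to 30%
- OTC-only use *q*: 10% to 30%
- share of OTC-only use captured by a returned form *k*: 50% to 100%
- form coverage *f*, set separately for cases and controls
- true laxative OR: 1

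Measured exposure = *r* + *q* × *k* × *f*.

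Apparent OR = [case exposure / (1 − case exposure)] ÷ [control exposure / (1 − control exposure)].

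*Equal coverage (50% in both groups).* Measured exposure is the same in both groups, so the OR is 1.00 for every *r*, *q* and *k*.

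*Coverage 50% in cases, 25% in controls:*
- Lowest value (*r* = 0.30, *q* = 0.10, *k* = 0.5). Cases: 0.30 + 0.10 × 0.5 × 0.50 = 0.325. Controls: 0.30 + 0.10 × 0.5 × 0.25 = 0.3125. OR = (0.325/0.675) ÷ (0.3125/0.6875) = 1.06.
- Highest value (*r* = 0.20, *q* = 0.30, *k* = 1.0). Cases: 0.20 + 0.30 × 1.0 × 0.50 = 0.350. Controls: 0.20 + 0.30 × 1.0 × 0.25 = 0.275. OR = (0.350/0.650) ÷ (0.275/0.725) = 1.42.

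*Coverage 60% in cases, 30% in controls.* The same calculation gives 1.07 to 1.50.

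**The case against.** The strongest objection is that the plan surveys controls as well as cases. Sections 9.2.1.3, 9.3.4 and 9.7.1 say so, and the negative predictive value criterion needs validated non-cases. The sampling allowance in Annex 3 applies to both groups. A reader might infer from the case-centred parts of section 9.3.4 that OTC use is ascertained more fully in cases by design. The documents do not support that: the section 9.9 rule makes no distinction by case status, and equal coverage produces no false association. For the same reason, a calculation with forms for every case and no control would contradict the plan.

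A reader might also infer that OTC use counts only when a form is returned. That is one reading of an ambiguous *and*; on the other, database-recorded OTC use counts for everyone.

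It can further be said that the methods sections already specify prescription records, that section 9.9 is a limitations section and the detail may sit in an analysis plan not shown here, that a form without an OTC item may capture little, and that the risk is disclosed.

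Much of this stands, and it rules out any claim of a built-in bias. Three things remain. Section 9.9 states what will be included, not merely a caveat, and it conflicts with three other sections of the same document. Unequal coverage is left open. Disclosure comes with no analysis to detect or limit the effect: the sensitivity analyses in section 9.7.3.1 vary the outcome status of unvalidated subjects, not the source of exposure. A form that captures little would reduce the bias, but it is also a reason not to use the form for this exposure.

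**Conclusion.** The point holds as an inconsistency in how a main exposure is defined, with an open but not prescribed route to differential measurement. The added source exists only for UK subjects with a returned form, and that form is poorly suited to OTC use at the index date.

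The size of any bias cannot be derived from the documents. The 1.06 to 1.42 range is an illustration. It depends on a true OR of 1, the assumed ranges for prescribed use, OTC-only use and capture, and above all on form coverage in cases being twice that in controls. With equal coverage and capture there is no bias from this route. This is a modest defect that is cheap to remove, and worth settling before the exposure variable is built.

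**What to change.** Amend section 9.9 so that laxative exposure in the main analysis comes only from the prescription or dispensing records available for every case and control in the database concerned, as sections 9.3.2, 9.7.2.1 and 9.7.3.1 already state. Use questionnaire-reported OTC laxatives only descriptively, or in a UK sensitivity analysis restricted to matched sets in which the case and its control or controls all have returned forms. If that analysis is run, state that the form records treatment at the IBS-C event date.

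The cost is one changed sentence and, if wanted, one restricted sensitivity analysis, which may be small given the low GP response. The downside is that total laxative use is somewhat more under-recorded, but cases and controls are then measured from the same source.
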